### **9.3.1. Prohibited therapy**

Prohibited treatments include the following:

- Other investigational drugs
- Concurrent anti-cancer therapies such as chemotherapy, gene therapy, biologics, radiation therapy, or immunotherapy

If any of these therapies are needed, the patient will be considered to have evidence of progressive disease. This will lead to the patient's discontinuation from the study.

### **9.3.2. Additional Anti-Cancer Treatment and Radiotherapy**

Patients should not receive additional therapeutic anti-cancer treatment until after PD has been documented on study and follow-up study assessments have been completed. If a patient requires additional anti-cancer treatment without radiological evidence of PD, the date of new treatment start will be considered the date of PD. If a patient stops study drug (atezolizumab) without evidence of PD, the patient will enter the Follow-up Period and followed every 3 months until PD.

### **9.3.3. Interaction of MV-NIS with Other Medications**

Drug-drug interaction studies have not been conducted on MV-NIS.

## 10. EFFICACY ASSESSMENTS

RECIST version 1.1 will be used in this study for assessment of tumor response. While either CT or MRI may be utilized as per RECIST 1.1, CT is the preferred imaging technique in this study.

Tumor measurements for efficacy evaluation will be done 5 weeks (36 day visit) after IT injection of the study drug and then every 3 cycles (i.e. cycles 4, 7, 10 etc.) until PD thereafter. A radiological assessment of CR or PR requires confirmatory imaging at least 4 weeks after the initial assessment of response was observed.

If there is suspicion of disease progression based on clinical or laboratory findings before the next scheduled assessment, an unscheduled assessment should be performed. Patients with a global deterioration of health status requiring discontinuation of treatment without objective evidence of disease progression at that time should be reported as “symptomatic deterioration”. Every effort should be made to document objective progression even after discontinuation of treatment.

For patients whose disease progresses, immune-related response criteria per irRECIST may be used by the investigator to continue therapy in the presence of potential pseudoprogression or tumor flare with clinical stability as appropriate until PD is confirmed.

For clinically stable patients, if imaging shows PD, treatment may be continued at the discretion of the investigator and tumor assessment should be repeated  $\geq$  9 weeks later to confirm or refute PD.

Clinically stable is defined by the following criteria:

- Absence of signs and symptoms indicating disease progression
- No decline in ECOG performance status
- Absence of rapid progression of disease
- Absence of progressive tumor at critical anatomical sites (e.g., cord compression) requiring urgent alternative medical intervention.

In determining whether the tumor burden has increased or decreased, investigators should consider all target lesions as well as nontarget lesions. Patients who are deemed clinically unstable are not required to have repeat imaging for confirmation. If radiologic progression is confirmed, then the patient will be discontinued from study treatment as specified in the protocol, and the first radiographic evidence of PD should be the date of progression. If radiologic progression is not confirmed, then the patient should resume/continue study treatment and have their next scan according to the protocol-specified schedule. If progression is not confirmed and the patient continues on treatment, the next scan that documents disease progression (and is confirmed by a second scan at least 4 weeks later), will be considered the date of disease progression.

If a patient with confirmed radiographic progression (i.e., 2 scans at least 28 days apart demonstrating progressive disease) is clinically stable or clinically improved, and there is no further increase in the tumor dimensions at the confirmatory scan, an exception may be considered to continue treatment upon consultation with the sponsor. Clinically stable patients should also have at the confirmatory scan no further increase in the target lesions, no

unequivocal increase in non-target lesions, and no additional new lesions develop (non-worsening PD) to continue study treatment.

Imaging during the follow-up period is to be repeated every 12 weeks ( $\pm$  7 days) for patients who discontinue study treatment for reasons other than disease progression until the end of the study.

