PD evaluation	
Tissue analysis for MV-NIS: Tumor biopsy is to be performed by radiologist post virus injection according to Table 1. Samples will be stored in:
 
 
RNAlater® for quantitative RT-PCR for MV-NIS RNA to determine copy numbers of virus/µg cellular RNA and RNASeq®
 
frozen sections for exome analysis
 
formalin-fixed paraffin embedded (FFPE) for pathology analysis (H&E and immune marker IHC).
 
 
Tissue analysis for tumor microenvironment: Tumor biopsy FFPE slides will be stained for immune markers including but not limited to CD3, CD4, CD8, CD14, CD20, and PD-L1.
 
Assessment of neoantigens and tumor-specific immune response: whole exome sequencing and RNA sequencing will be performed from normal tissue (PBMCs) and tumor biopsy samples obtained before and ~2 weeks after MV-NIS injection. Detailed bioinformatics analysis will be undertaken to determine mutational/antigen profiles. Identification of candidate 9-10 amino acid peptides containing mutations predicted to bind with high affinity to patients' MHC Class I molecules will be done by using the Immune Epitope Database prediction algorithm. Chosen peptides will be synthesized and used to prepare MHC fluorescent tetramers for their use for flow cytometry of patient peripheral T cells and/or TILs to determine frequency of tumor specific T cells pre and post therapy. In addition, functional assays of T cells will be performed by IFN-gamma release assays.

Efficacy	
RECIST v1.1 will be used to assess anti-tumor efficacy for the secondary efficacy endpoint. An exploratory analysis using irRECIST will also be performed.
 
irRECIST will be used for defining progressive disease (PD) on study as follows to account for the possibility of pseudoprogression or tumor flare. Patients should be reevaluated for disease response every 9 weeks after cycle 1 (i.e. at end of cycles 4, 7, 10, etc).
 
For clinically stable patients, if imaging shows PD, treatment may be continued and tumor assessment should be repeated ≥ 9 weeks later to confirm or refute PD. Clinically stable is defined by the following criteria:

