5. Biopsies to be obtained by radiologist under CT guidance. Pre-treatment biopsy will be of lesion planned for MV-NIS injection. Biopsy 12-15 days post-MV-NIS injection will be after SPECT/CT imaging but before atezolizumab administration and include 6 core biopsies of the MV-NIS-injected lesion and 6 core biopsies of an uninjected lesion (if feasible). See lab manual for further details and prioritization of processing in the case of insufficient material. Biopsies of injected lesion and an uninjected lesion may be repeated at day 36 (+/- 5 days) if feasible. Biopsies for a) paraffin sections, b) exome and RNA sequencing, c) infectious virus recovery, d) qRT-PCR for viral RNA. Exome sequencing only at baseline. See lab manual for details on processing and collection.
6. Mouth swab and urine collection for shedding studies by infectious virus recovery. See lab manual for details on processing and collection.
7. Assessment of viremia: Collect 2.5 ml blood into PAXgene tube (2 tubes). Perform at day 3, 15 and 36 (if day 15 is positive). If at day 36, there is 10-fold increase in MV-NIS/mcg of RNA, repeat tests will be performed within 2 days to confirm the result. Weekly testing will be done thereafter until resolution to baseline. See lab manual for details.
8. Research blood for a) immune phenotyping by flow cytometry, b) PBMC for exome and RNA sequencing, c) T cell analysis for neoantigen and tetramer assays. Exome sequencing done only at baseline. See lab manual for processing and collection.
9. Day 15 visit may be split into 2 visits to permit flexibility in biopsy timing and recovery prior to atezolizumab treatment as follows: Day 12-15 SPECT/CT, viral shedding, viremia, research blood for flow cytometry, PBMCs for sequencing and T cell assay must be performed PRIOR to tumor biopsy; Day 15-16 physical exam, history, vitals, PS and atezolizumab administration.
10. After Cycle 1, tumor measurements per RECIST 1.1 will be conducted every 3 cycles (i.e. cycles 4, 7, 10 etc.) until PD. For patients whose disease progresses, immune-related response criteria may be used by the investigator to continue therapy in the presence of potential pseudoprogression or tumor flare with clinical stability as appropriate until PD is confirmed.
11. Patients who discontinue atezolizumab for reasons other than disease progression will continue to have tumor evaluations every 12 weeks per standard of care until PD.

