### **9.1.7. Dose Modifications and Delays for Toxicity Related to Study Drug**

Since there is only one dose of MV-NIS administered per patient, there are no dose modifications or delays in this study for MV-NIS. If the patient experiences an acute injection or procedure related reaction the procedure should be abandoned and supportive care provided. If study drug administration is abandoned due to technical reasons not associated with an AE, the procedure may be reattempted at another time at the investigators discretion. Consult the medical monitor regarding reassessment of eligibility in such cases.

Dose modifications and delays for atezolizumab should be based on the approved [Tecentriq® US Package Insert](#).

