### 5.3 Immune-Related Colitis

Immune-mediated colitis or diarrhea, defined as requiring use of corticosteroids and with no clear alternate etiology, occurred in patients receiving TECENTRIQ. Monitor patients for signs and symptoms of diarrhea or colitis. Withhold treatment with TECENTRIQ for Grade 2 diarrhea or colitis. If symptoms persist for longer than 5 days or recur, administer 1–2 mg/kg prednisone or equivalent per day. Withhold treatment with TECENTRIQ for Grade 3 diarrhea or colitis. Treat with IV methylprednisolone 1–2 mg/kg per day and convert to oral steroids once the patient has improved. For both Grade 2 and Grade 3 diarrhea or colitis, when symptoms improve to Grade 0 or Grade 1, taper steroids over  $\geq$  1 month. Resume treatment with TECENTRIQ if the event improves to Grade 0 or 1 within 12 weeks and corticosteroids have been reduced to the equivalent of  $\leq$  10 mg oral prednisone per day. Permanently discontinue TECENTRIQ for Grade 4 diarrhea or colitis [see *Dosage and Administration (2.2) and Adverse Reactions (6.1)*].

Across clinical trials, colitis or diarrhea occurred in 19.7% (389/1978) of all patients.

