## NSCLC

The safety of TECENTRIQ was evaluated in Study 3, a multi-center, international, randomized, open-label trial in patients with metastatic NSCLC who progressed during or following a platinum-containing regimen, regardless of PD-L1 expression [see *Clinical Studies (14.2)*]. Patients received 1200 mg of TECENTRIQ (n=142) administered intravenously every 3 weeks until unacceptable toxicity or either radiographic or clinical progression or docetaxel (n=135) administered intravenously at 75 mg/m^2 every 3 weeks until unacceptable toxicity or disease progression. The median duration of exposure was 3.7 months (range: 0–19 months) in TECENTRIQ-treated patients and 2.1 months (range: 0–17 months) in docetaxel-treated patients.

The most common adverse reactions ( $\geq 20\%$ ) in patients receiving TECENTRIQ were fatigue (46%), decreased appetite (35%), dyspnea (32%), cough (30%), nausea (22%), musculoskeletal pain (22%), and constipation (20%). The most common Grade 3-4 adverse reactions ( $\geq 2\%$ ) were dyspnea, pneumonia, hypoxia, hyponatremia, fatigue, anemia, musculoskeletal pain, AST increase, ALT increase, dysphagia, and arthralgia.

Nine patients (6.3%) who were treated with TECENTRIQ experienced either pulmonary embolism (2), pneumonia (2), pneumothorax, ulcer hemorrhage, cachexia secondary to dysphagia, myocardial infarction, or large intestinal perforation which led to death.

TECENTRIQ was discontinued due to adverse reactions in 4% (6/142) of patients. Adverse reactions leading to interruption of TECENTRIQ occurred in 24% of patients; the most common ( $>1\%$ ) were pneumonia, liver function test abnormality, upper respiratory tract infection, pneumonitis, acute kidney injury, hypoxia, hypothyroidism, dyspnea, anemia, and fatigue. Serious adverse reactions occurred in 37% of patients. The most frequent serious adverse reactions ( $> 2\%$ ) were pneumonia, dyspnea, pleural effusion, pyrexia, and venous thromboembolism.

Table 3 summarizes adverse reactions that occurred in at least 10% of TECENTRIQ-treated patients and at a higher incidence than in the docetaxel arm. Table 4 summarizes selected laboratory abnormalities worsening from baseline that occurred in  $\geq 10\%$  of TECENTRIQ-treated patients and at a higher incidence than in the docetaxel arm.

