## 14.2 Metastatic Non-Small Cell Lung Cancer

### Previously Treated Metastatic NSCLC

The efficacy of TECENTRIQ was investigated in two multi-center, international, randomized, open-label trials in patients with metastatic NSCLC who progressed during or following a platinum-containing regimen. Study 2 was a trial in 1225 patients with the primary analysis population consisting of the first 850 randomized patients and Study 3 was a trial in 287 patients. In both studies, eligible patients were stratified by PD-L1 expression status in tumor-infiltrating immune cells (IC), by the number of prior chemotherapy regimens, and by histology. Patients

were randomized (1:1) to receive either TECENTRIQ administered intravenously at 1200 mg every 3 weeks until unacceptable toxicity or either radiographic or clinical progression or docetaxel administered intravenously at 75 mg/m^2 every 3 weeks until unacceptable toxicity or disease progression. These studies excluded patients who had: a history of autoimmune disease, had active or corticosteroid-dependent brain metastases, administration of a live, attenuated vaccine within 28 days prior to enrollment, administration of systemic immunostimulatory agents within 4 weeks or systemic immunosuppressive medications within 2 weeks prior to enrollment. Tumor assessments were conducted every 6 weeks for the first 36 weeks, and every 9 weeks thereafter. In Study 2, tumor specimens were evaluated prospectively for PD-L1 expression on tumor cells (TC) and IC using the VENTANA PD-L1 (SP142) Assay and the results were used to define the PD-L1 expression subgroups for the analyses described below.

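### Tumour scans after Day 36 are counted in atezolizumab cycles in three places and in weeks in the synopsis; nothing says which governs when a dose is held

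*Combined protocol and SAP*

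**What the plan says.** Section 10 sets the first on-study scan at Day 36 and later ones "then every 3 cycles (i.e. cycles 4, 7, 10 etc.) until PD thereafter". Table 1 footnote 10 uses the same unit: "After Cycle 1, tumor measurements per RECIST 1.1 will be conducted every 3 cycles (i.e. cycles 4, 7, 10 etc.) until PD". Section 12.1.12.2 repeats it. In the Table 1 grid, the later tumour measurements and the atezolizumab infusions share one column, headed as day 1 of each further 21-day cycle.

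The Efficacy row of the synopsis gives a number of weeks: "Patients should be reevaluated for disease response every 9 weeks after cycle 1 (i.e. at end of cycles 4, 7, 10, etc".

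Dose delays are foreseen. Section 9.1.7 says: "Dose modifications and delays for atezolizumab should be based on the approved" US label. That label (Appendix 2, section 2.2) lists events for which dosing is withheld. For colitis it says: "Resume treatment with TECENTRIQ if the event improves to Grade 0 or 1 within 12 weeks", with a further condition on steroid dose. It uses the same 12-week limit for adrenal insufficiency and pancreatitis.

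No section says whether a held dose moves the cycle number, or whether the scan date follows the cycle or the calendar.

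**The concern.** Table 1 puts the scan and the infusion under the same cycle day. A site can therefore reasonably take the cycle to start with the dose, and the scan to wait when the dose waits. On that reading the gap between scans depends on whether dosing was held. Progression is dated at the scan that shows it, so a longer gap dates silent progression later.

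PFS and DOR are secondary endpoints. Section 6.3 also plans to relate them to immune markers and to compare them with historical controls. With a single arm, no concurrent group would show that scan spacing had drifted.

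There is also an internal oddity. Section 10 images patients who stop treatment without progression every 12 weeks by calendar. If cycles slip, a patient who is only held waits 9 + h weeks, which is longer than 12 weeks for any hold above 3 weeks.

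**Working it through.** **Inputs from the documents.** First atezolizumab dose on Day 15; 21-day cycles; Day 36 is cycle 2 day 1; scans tied to cycles 4, 7 and 10; 9-week spacing in the synopsis; 24% of atezolizumab patients interrupted (label, Study 3).

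**Inputs assumed.** Holds of 3, 6 or 12 weeks; exponential true PFS with a median of 2 to 6 months. The documents give neither.

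**1. The plan's own 9 weeks.** Day 1 of cycle n = 15 + 21(n − 1).
- Cycle 2 day 1 = 15 + 21 = Day 36, as in Table 1.
- Cycle 4 ends when cycle 5 would begin: 15 + 84 = Day 99, and 99 − 36 = 63 days = 9 weeks. Likewise cycle 7 ends at Day 162 and cycle 10 at Day 225.
- Cycle 4 day 1 = 15 + 63 = Day 78, which is 42 days = 6 weeks after Day 36.

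The synopsis figure is therefore reproduced when no dose is delayed and the scan falls at the end of the cycle. The other passages omit that qualifier, and the Table 1 column points to day 1 of the cycle. This leaves a second ambiguity, Day 78 versus Day 99.

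**2. Effect of a hold if cycles move with dosing.** Interval = 9 + h weeks. Mean lateness = interval / 2, taking progression as uniform within the interval.

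| Hold (weeks) | Interval (weeks) | Mean lateness (weeks) |
|---|---|---|
| 0 | 9 | 4.5 |
| 3 | 12 | 6.0 |
| 6 | 15 | 7.5 |
| 12 | 21 | 10.5 |

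On the Day 78 reading the first gap is 6 weeks, and the same holds stretch it to 9, 12 or 18 weeks.

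**3. How many patients.** The label states: "Adverse reactions leading to interruption of TECENTRIQ occurred in 24% of patients". 0.24 × 21 = 5.04, about 5. This is an upper figure, because interruptions of any length are counted and some would move no scan.

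**4. Effect on recorded PFS.** Simulation with scans on Days 36, 99, 162 and so on, one hold placed between Day 36 and the next scan, no deaths and no unscheduled scans. The range runs over true medians of 2 to 6 months.

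| Hold (weeks) | Rise in mean PFS, held patients (days) | Rise over all patients, 24% held (days) |
|---|---|---|
| 3 | 2.7 to 5.5 | 0.7 to 1.3 |
| 6 | 6.7 to 12.8 | 1.6 to 3.1 |
| 12 | 17.8 to 31.3 | 4.2 to 7.5 |

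With 24% held, the observed median does not move at true medians of 2, 4 or 6 months. At 3 months it jumps from Day 99 to Day 120, 141 or 162, because the true median lies close to a scan day.

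**5. What does not change.** The response rule (at least 8 of 21; 20% versus 45%) reproduces as alpha 0.043 and power 80.29% by the exact binomial. It does not depend on how held doses are handled.

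**The case against.** **The delay is conditional.** No passage says a held dose renumbers the cycle. Table 1 speaks of 21-day cycles, and the synopsis equates the cycle labels with 9 weeks. If either runs by calendar, a hold moves nothing. This stands: the documents support an unreconciled inconsistency, not a certain delay.

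**Safeguards exist.** Day 36 is counted from the injection, patients who stop without progression are scanned by calendar, and Section 10 calls for an unscheduled scan when progression is suspected. This stands too. What remains exposed is progression without symptoms or laboratory signs during a hold, and the simulation, which has no unscheduled scans, overstates the lateness.

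**Long holds should be uncommon.** Twelve weeks is a limit for resuming, named for a few events. The label reports immune-mediated colitis or diarrhoea in 0.5% of NSCLC patients, adrenal insufficiency in 0.4% and symptomatic pancreatitis in 0.1% across trials. The 24% and the 12 weeks should not be combined as the expected case.

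**A stronger reading is not supported.** A reader might infer that immune toxicity would appear to go with longer disease control. No analysis of toxicity against efficacy is planned; Section 6.3 relates efficacy to PD-L1 and immune markers. Such a bias would further require that those markers predict holds.

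**The historical contrast is thin.** In the label's NSCLC trials, "Tumor assessments were conducted every 6 weeks for the first 36 weeks, and every 9 weeks thereafter". The label does not say how holds were handled there, and it reports no PFS for those trials. Their 6-week early spacing differs from 9 weeks even with no hold.

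**Conclusion.** The narrower point holds. Three passages count scans in cycles, one counts in weeks, delays are allowed, and no rule links them. If cycles slip with dosing, the interval containing a hold grows by the length of the hold, and silent progression can be dated later in held patients. A reader might take this to mean that progression is found late in exactly the patients with toxicity. The documents do not support that: many toxicities cause no hold, and suspected progression prompts a scan.

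The effect on mean PFS in held patients is a few days for a 3-week hold and about 18 to 31 days for a 12-week hold in the first gap. Over all patients it is about 1 to 7 days. These figures rest on the assumed hold lengths and PFS medians, and on leaving out unscheduled scans. The direction for DOR is not fixed, because a hold before first response also delays the recorded start of response. The MTD and the response rule are untouched. The matter concerns secondary and exploratory PFS and DOR only, and is one to consider.

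**What to change.** In Section 10, Table 1 footnote 10 and Section 12.1.12.2, and consistently in the synopsis and the Table 1 grid, state that tumour scans follow the calendar from Day 1: Day 36, then every 9 weeks (Days 99, 162, 225 and so on), irrespective of atezolizumab delays. Add a window, such as the 7 days either side already used for follow-up imaging. Say explicitly that this also settles start versus end of cycle, with Day 99 and not Day 78 as the second on-study scan, in line with the synopsis.

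The change is to wording. It alters no dosing rule and adds no scan beyond the 9-weekly ones the synopsis already plans. Some scans will not coincide with an infusion visit. If sites now scan on Day 78, moving to Day 99 has a small price for every patient: mean lateness after Day 36 rises from about 4.4 to 4.7–4.9 weeks, assuming exponential PFS with a median of 3 to 6 months. The sponsor should make that choice knowingly.

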### **Baseline Eligibility**

Measurable Disease:	
Tumor lesions: Must be accurately measured in at least one dimension (longest diameter in the plane of measurement is to be recorded) with a minimum size of:
 
 
• 10 mm by CT by computerized tomography (CT scan slice thickness no greater than 5 mm).
 
• 10 mm caliper measurement by clinical exam (lesions that cannot be accurately measured with calipers should be recorded as non-measurable).
 
• 20 mm by chest x-ray.
 
 
Skin lesions: Documentation by color photography, including a ruler to estimate the size of the lesion, is recommended.
 
Malignant lymph nodes: To be considered pathologically enlarged and measurable, a lymph node must be <math>\geq 15</math> mm in short axis when assessed by CT scan. At baseline and in follow-up, only the short axis will be measured and followed.

Non-Measurable Disease:	All other lesions, including small lesions (longest diameter $<10$ mm or pathological lymph nodes with $\geq 10$ to $<15$ mm short axis) as well as truly non-measurable lesions. Lesions considered truly non-measurable include: leptomeningeal disease, ascites, pleural or pericardial effusion, inflammatory breast disease, and lymphangitic involvement of skin or lung, abdominal masses, abdominal organomegaly identified by physical exam that is not measurable by reproducible imaging techniques.
Target Lesions:	
The most reproducible measurable lesions, up to a maximum of 2 lesions per organ and 5 lesions in total, representative of all involved organs should be identified as target lesions and recorded and measured at baseline.
 
Target lesions should be selected on the basis of their size (lesions with the longest diameter), should be representative of all involved organs, and, in addition, should be those that lend themselves to reproducible repeated measurements. Pathological nodes which are defined as measurable and that may be identified as target lesions must meet the criterion of a short axis of <math>\geq 15</math> mm. All target lesions will be calculated and reported as the baseline sum diameters. If lymph nodes are to be included in

	the sum, then as noted above, only the short axis is added into the sum. The baseline sum diameters will be used as reference to further characterize any objective tumor response.
Non-Target Lesions:	All other lesions (or sites of disease) are identified as non-target lesions (chosen based on their representativeness of involved organs and the ability to be reproduced in repeated measurements) and should be recorded at baseline. Measurements of these lesions are not required, but the presence or absence of each should be noted throughout follow-up. Lymph nodes with short axis $\geq$ 10mm but $<$ 15mm should be considered non-target lesions. Nodes that have a short axis $<$ 10mm are considered non-pathological and are not recorded or followed.

